## 9.1 Correlations

The association and correlation, respectively, of MSOT parameters versus clinical/angiographic outcomes (secondary endpoints) is calculated appropriate measures of association and correlation, e.g. differences in mean, or Pearson's or Spearman's rank correlation coefficients.

## 9.2 Differences in Severity of PAD

Overall differences of MSOT readouts vs. the PAD stages will be statistically tested using ANOVA including a post hoc Tukey test, comparing all three pairs deriving a 95% family-wise confidence level of differences between means.

## 9.3 Sensitivity and Specificity

Using the cutpoint maximising the Youden index derived from study group 1 based on controls vs. PAD classes III/IV, the diagnostic properties of MSOT values will be illustrated by sensitivity and specificity (with 95% CI) associated with a diagnostic test decision dichotomised at that cutpoint. The same cutpoint will be employed in study group 2 for validation of diagnostic properties.

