#### *Primary objectives:*

- Study group 1: Derivation of optimal diagnostic MSOT thresholds for hemoglobin through correlation with TASC classification for angiographic imaging (and CCDS if necessary) as references for relevant stenosis/occlusion in patients with PAD.

---

 Angiographic images are reviewed by two independent and experienced individuals to determine the type of TASC.

In the TASC classification for angiographic imaging, the pelvic and femoral arteries are assessed separately based on the extent and localization of the present stenoses/occlusions. However, the perfusion situation in the target region (calf muscle), that is measured by MSOT, results from a combination of both findings. In order to represent the circulation situation in the target muscle properly and to enable a correlation with the MSOT parameters measured there, it is necessary to regard the existing aorto-iliac and femoro-popliteal constellations of findings. For this purpose, 3 categories are established (1 – 3), that result from the occurring combinations of findings of both TASC classifications. The description of the categories can be found in the Statistical Analysis Plan (version 1.1, 01/20/2022).

- Study group 2: Validation of the diagnostic accuracy of MSOT, employing the cut-off values derived in study group 1, in terms of MSOT hemoglobin values through correlation with TASC classification for angiographic imaging as a reference of relevant stenosis/occlusion in patients with PAD in an independent cohort.

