## 4 Hypothesis, Study Objectives and Endpoints

### 4.1 Hypothesis to be statistically tested

The hypothesis is that MSOT can predict clinical and angiographic disease severity in patients with PAD.

- H0: MSOT parameters are not associated with angiographic manifestations
- H0: MSOT parameters do not differ between healthy subjects and patients with PAD (graded according to angiographic classifications)

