### 4.2 Objectives

#### Primary objectives

- Study group 1: Derivation of optimal diagnostic MSOT thresholds for hemoglobin through correlation with TASC classification for angiographic imaging (and CCDS if necessary) as references for relevant stenosis/occlusion in patients with PAD
- Study group 2: Validation of the diagnostic accuracy of MSOT, employing the cut-off values derived in study group 1, in terms of MSOT hemoglobin values through correlation with TASC classification for angiographic imaging as a reference for relevant stenosis/occlusion in patients with PAD in an independent cohort

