## 9 Diagnostic Performance Analysis

Diagnostic performance will be examined in different successive steps: first, distribution of single MSOT readouts within the different PAD stages used as external criterion (gold standard) will be assessed. Second, the difference in means of the (MSOT) readouts between patient subgroups will be assessed and statistically tested. If significant, these readouts will be subject to a ROC analysis to determine the optimum cutpoint; further details see below.

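### SAP 9.3 derives the primary cutpoint from controls versus PAD III/IV, whereas the primary objectives require angiographic TASC as the reference

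*SAP*

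**What the plan says.** The primary endpoint (SAP 4.3) is the optimal diagnostic MSOT threshold for hemoglobin. The group 1 objective in SAP 4.2 is "Derivation of optimal diagnostic MSOT thresholds for hemoglobin through correlation with TASC" classification "for angiographic imaging (and CCDS if necessary) as references for relevant stenosis/occlusion in patients with PAD". The group 2 objective is to validate accuracy "in terms of MSOT hemoglobin values through correlation with TASC classification for angiographic imaging as a reference for relevant stenosis/occlusion". Protocol 5.1 says the same. Its footnote sets up three categories "that result from the occurring combinations of findings of both TASC classifications", which SAP 5.4 defines as aTASC 1 to 3. The second null hypothesis in SAP 4.1 is that "MSOT parameters do not differ between healthy subjects and patients with PAD (graded according to angiographic classifications").

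The analysis sections are built on stage. SAP 9 begins with the "distribution of single MSOT readouts within the different PAD stages used as external criterion (gold standard) will be assessed". SAP 9.2 states: "Overall differences of MSOT readouts vs. the PAD stages will be statistically tested using ANOVA". SAP 9.3 fixes the cutpoint: "Using the cutpoint maximising the Youden index derived from study group 1 based on controls vs. PAD classes III/IV". It then applies the same cutpoint in group 2 without naming a reference for that step.

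Other sections also bear on the point:
- SAP 3.2, the lead sentence of SAP 4.1, and SAP 7.3 name clinical severity beside angiography. The primary objectives do not.
- SAP 12.6 has a shell for MSOT sensitivity and specificity by combined TASC subgroup. It gives no positive/negative split, and its companion table has four columns (I-IV).
- SAP 7.2, 7.4 and 8.2 make all eligible participants the default analysis set, with exclusion from a sub-analysis when a value is missing.

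**The concern.** The objectives and the derivation rule name different target conditions. An analyst who follows 9.3 will report a threshold that separates volunteers from patients with rest pain or trophic lesions. The objective asks for one that detects angiographically relevant stenosis or occlusion in the stage II-IV patients the study enrols.

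Two things are at stake. First, accuracy from the two ends of the spectrum may be read as accuracy across stages II-IV. Second, 9.3 does not say whether stage II counts in the group 2 estimate, which reference defines disease there, or which aTASC categories are positive. The validation result then depends on a choice (for example aTASC 1 versus 2-3, or 1-2 versus 3) that could be made after the data are seen.

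**Working it through.** **1. What III/IV means.** SAP 5.4 defines Fontaine III and IV by symptoms, and SAP 6 pools exactly these two stages as critical ischemia. If III/IV meant columns III and IV of shell 12.6, it would be undefined, because only three aTASC classes exist. Fontaine is therefore the natural reading, and the text needs correction on either reading.

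**2. Whether stage can stand in for aTASC.** By the SAP 5.4 table, femoro-popliteal TASC D with no finding or A/B at aorto-iliac level is aTASC 2. Aorto-iliac C/D with no femoro-popliteal finding is aTASC 3. Symptoms play no part in separating these classes, so Fontaine stage and aTASC are not interchangeable.

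**3. Share of PAD patients outside the derivation.**
- SAP 6 sizes three equal groups (healthy, II, III-IV). Stage II is 33/(33+33) = 50% for Hb and 11/(11+11) = 50% for HbO2.
- SAP 5.2 expects similar sizes for IIa, IIb, III and IV: 2/4 = 50%.
- The accrual figures in SAP 6 give 102 − 33 − 29 = 40 and 40/(40+29) = 58%. This holds only if all 102 fall in these three groups and belong to group 1; both are assumptions.

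**4. Implied effect sizes.** The SAP gives no means or SDs, so its sample sizes cannot be reproduced independently. They can be inverted. With one-sided alpha 0.05 and 80% power, the normal approximation is d = √(2/n) × (1.645 + 0.842):
- n = 33: d = 0.612
- n = 11: d = 1.060

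A two-sample t-test (assumed; the SAP names no test) gives d = 0.619 and 1.098, which are used below. Nothing here suggests an error in the stated numbers.

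**5. Spectrum illustration.** Assume controls N(0,1), III/IV N(d,1), stage II N(f·d,1) with f assumed at 0.25 to 0.75, and all patients counted as positive. The Youden cutpoint for controls versus III/IV is c = d/2 = 0.309 / 0.549 (Hb / HbO2).
- Sensitivity in III/IV = specificity = Φ(d/2) = 62% / 71%.
- Sensitivity over all PAD, with share w in stage II = w·Φ(f·d − c) + (1 − w)·Φ(d − c).

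| Stage II shift f | All-PAD sensitivity, w = 50% | w = 58% |
|---|---|---|
| 0.75 | 59.1% / 65.8% | 58.7% / 65.0% |
| 0.50 | 56.1% / 60.4% | 55.1% / 58.8% |
| 0.25 | 53.0% / 55.0% | 51.5% / 52.5% |

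**6. How far the cutpoint is off.** Re-maximise the Youden index over all PAD with w = 50% and f = 0.5.
- The cutpoint moves to 0.257 / 0.451, a shift of 0.053 / 0.098 SD.
- All-PAD sensitivity becomes 58.1% / 64.0% and specificity 60.1% / 67.4%.
- The Youden index rises from 0.182 to 0.183 (Hb) and from 0.313 to 0.314 (HbO2).

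Across f = 0.25 to 0.75 at w = 50%, the shift is 0.03-0.05 / 0.06-0.10 SD. With w = 58% and f = 0.5 it is 0.064 / 0.119 SD. The Youden gain is at most 0.002 in every scenario.

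**7. What cannot be computed.** The documents give no MSOT values by TASC class and no cross-table of stage by aTASC. The effect of replacing TASC by stage therefore has no number.

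**The case against.** The strongest reply is that the SAP as a whole does not set angiography aside. The hypothesis, the purpose and the reference-standard subgroups all name clinical severity as well, and shell 12.6 already plans accuracy by combined TASC subgroup. This stands: the conflict is between 9.3 and the primary objectives. A reader might infer that angiographic accuracy has been dropped from the plan, and shell 12.6 shows that it has not. But that shell gives no dichotomy, and its companion table has four columns for three classes.

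A reader might also infer that the threshold is certainly derived for one condition and validated against another. Section 9.3 names no group 2 reference, so that follows only when 9.3 is read together with the group 2 objective. If 9.3 carries its own contrast into group 2, derivation and validation agree with each other and both miss the objective.

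Nor is the plan silent on who is analysed. All eligible participants are the default, and the III/IV restriction attaches only to the group 1 derivation. What stays open is whether stage II counts in the group 2 accuracy estimate and what defines disease there. The split aTASC 1 versus 2-3 is the natural reading of SAP 5.4, since aTASC 1 is the healthy type, but it is nowhere stated.

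Finally, III/IV may be a leftover label from a four-class TASC scheme. That is possible but less likely, and it would still need correcting.

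**Conclusion.** The concern holds as a mismatch between the primary objectives and the only derivation rule. As written, the reported threshold and accuracy would describe healthy versus critical ischemia, not relevant stenosis or occlusion on angiography in stages II-IV. About half of PAD patients, on the planned group sizes, do not enter the derivation.

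It is tempting to conclude that the cutpoint itself is materially wrong. The illustration does not support that: a move of about 0.03-0.10 SD and a Youden gain of at most 0.002. What changes is the accuracy that can be claimed, 62% / 71% sensitivity in III/IV against 53-59% / 55-66% over all PAD with half in stage II. Those figures rest on a binormal equal-variance model, an assumed t-test behind n = 33 and n = 11, and assumed stage II shifts. The finding about the target condition rests on the text alone. This should be fixed before the final analysis.

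**What to change.** - **SAP 9.3, derivation.** Define the primary cutpoint in group 1 against one prespecified aTASC dichotomy, for example aTASC 1 versus 2-3. Use volunteers and all stage II-IV patients with an angiogram less than 12 months from the index test. State when CCDS is used.
- **SAP 9.3, validation.** Apply the locked cutpoint in group 2 with the same dichotomy and the same population definition.
- **Secondary analyses.** Keep controls versus III/IV, labelled as secondary. Report sensitivity separately for stage II and stage III-IV. Add an analysis in imaged participants only, for example aTASC 2 versus 3. It is needed because unimaged volunteers are aTASC 1 by rule, so aTASC 1 versus 2-3 stays close to volunteers versus all PAD.
- **Consistency.** Align SAP 9, SAP 9.2 and the columns of shell 12.6 with the chosen reference.

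No new measurements are needed. The costs should be stated. Reported accuracy will probably be lower. Patients whose angiogram is 12 months old or older drop out of the primary analysis. The sample size was not set for this contrast. Healthy versus III/IV data were already used for sizing (SAP 6), so the change should be dated and documented as made after that use.

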### 4.3 Endpoints

#### Primary endpoint

- Optimal diagnostic MSOT thresholds [Time Frame: single time point (1 day)]: Optimal diagnostic thresholds for hemoglobin values in muscle tissue determined by MSOT in patients with PAD

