**6 Determination of Sample Size**

Based on the data collected until 05.03.2021 the case number calculation (no interim analysis) was performed in cooperation with the Institute of Biometry. Six of a total of 102 persons included up to the above-mentioned date were diagnosed with PAD stage III according to Fontaine. In the course of the study, it became apparent that a sample size calculation based on 30 patients with stage III disease and 30 healthy subjects, as initially planned, could not be realised during a realistic time period.

In order to establish a valid case number as early as possible, the two critical PAD stages III and IV were formally combined into one group to be considered together as chronic critical limb ischemia. Thus, based on the results of a total of 33 healthy study subjects and 29 subjects diagnosed with a critical PAD stage, the exemplary case number calculation could be accomplished. A power analysis, which allowed a power of 80% at an alpha of 0.05 (unilateral) was performed to determine the final sample size. For the MSOT parameter deoxygenated hemoglobin, the number of subjects was approximately 33, and for the MSOT parameter oxygenated hemoglobin, the number of subjects was approximately 11 for each of the individual groups (healthy control group, PAD stage II, PAD stage III-IV).

Dropout is not considered because the study is performed during a single visit.

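### The primary endpoint is a threshold, but SAP 9.3 plans no confidence interval for it, and a Youden cutpoint is imprecise at every group size the plan suggests

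*SAP*

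**What the plan says.** SAP 4.3 defines the primary endpoint as "Optimal diagnostic thresholds for hemoglobin values in muscle tissue determined by MSOT in patients with PAD". SAP 9 admits readouts to cutpoint selection through a test of group means: "If significant, these readouts will be subject to a ROC analysis to determine the optimum cutpoint". SAP 9.3 describes the selection as "Using the cutpoint maximising the Youden index derived from study group 1 based on controls vs. PAD classes III/IV". Performance is then "illustrated by sensitivity and specificity (with 95% CI) associated with a diagnostic test decision dichotomised at that cutpoint". For study group 2, "The same cutpoint will be employed in study group 2 for validation of diagnostic properties".

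The cutpoint receives no interval in SAP 9, in the reporting convention (SAP 10) or in the sample tables (SAP 12). SAP 9.3 does not say whether the Youden index is maximised on the empirical ROC curve or on a fitted one.

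SAP 6 and protocol 8.2 size the study for a difference between groups at 80% power and one-sided alpha 0.05: "For the MSOT parameter deoxygenated hemoglobin, the number of subjects was approximately 33", and about 11 for oxygenated hemoglobin, in each group. No mean, SD or AUC is given.

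**The concern.** When the endpoint is an estimated quantity, its standard error or interval belongs to the result. Here the intervals are attached to sensitivity and specificity at a cutpoint treated as known. The empirical Youden cutpoint is the location of the peak of a step function that is nearly flat around its maximum, so it can move a long way from sample to sample while the peak height hardly changes.

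The cutpoint is the one quantity carried from study group 1 to study group 2. If its uncertainty is not shown, a reader will take both the threshold in arbitrary units and the resulting balance of sensitivity and specificity as properties of MSOT. A second centre deriving a cutpoint the same way could obtain a very different one.

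**Working it through.** **1. Effect sizes (assumption).** The plan's sample size cannot be reproduced independently, because no effect size is stated. Inverting it for two equal-variance normal groups:

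n = 2(z₀.₉₅ + z₀.₈₀)²/d² = 2(1.645 + 0.842)²/d² = 12.37/d²

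- n = 33 gives d = √(12.37/33) = 0.61, or 0.62 with the t distribution (Hb).
- n = 11 gives d = √(12.37/11) = 1.06, or 1.10 with the t distribution (HbO2).

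**2. Best attainable accuracy.** In control-SD units the true Youden cutpoint is d/2, with sensitivity = specificity = Φ(d/2). For Hb this is Φ(0.31) = 62%, Youden index 0.24. For HbO2 it is Φ(0.55) = 71%, Youden index 0.42.

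**3. Sizes (assumption).** SAP 6 suggests 33 or 11 per group. SAP 5.2 anticipates about 200 subjects in five similar groups: 200/5 = 40 controls and 2 × 40 = 80 PAD III/IV in the whole study, or 20 versus 40 if halved between the study groups.

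**4. Simulation.** 10,000 runs per scenario: select the empirical Youden cutpoint c, then compute its true sensitivity Φ(d − c) and specificity Φ(c). Ranges are central 95%. Cutpoints are in control SDs, oriented so that higher values mean disease.

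| Readout | Controls vs III/IV | SD of c | Range of c | True sensitivity | True specificity | Mean true Youden |
|---|---|---|---|---|---|---|
| Hb, d = 0.62 | 11 vs 11 | 0.63 | −1.03 to 1.45 | 20–95% | 15–93% | 0.21 |
| | 20 vs 40 | 0.52 | −0.75 to 1.28 | 25–92% | 23–90% | 0.22 |
| | 33 vs 33 | 0.49 | −0.68 to 1.23 | 27–90% | 25–89% | 0.22 |
| | 40 vs 80 | 0.44 | −0.60 to 1.13 | 31–89% | 28–87% | 0.22 |
| HbO2, d = 1.10 | 11 vs 11 | 0.51 | −0.54 to 1.48 | 35–95% | 30–93% | 0.38 |
| | 20 vs 40 | 0.40 | −0.30 to 1.26 | 44–92% | 38–90% | 0.39 |
| | 33 vs 33 | 0.38 | −0.21 to 1.29 | 43–91% | 42–90% | 0.39 |
| | 40 vs 80 | 0.32 | −0.11 to 1.15 | 48–89% | 46–87% | 0.40 |

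Hand check, Hb at 33 vs 33: c = −0.68 gives sensitivity Φ(1.30) = 90% and specificity Φ(−0.68) = 25%; c = 1.23 gives Φ(−0.61) = 27% and Φ(1.23) = 89%.

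A separate repeat gave 28–91% (Hb) and 47–91% (HbO2) at 33 vs 33, and 32–89% and 49–89% at 40 vs 80. Monte Carlo error and the rule for tied maxima move the ends by up to about 4 points.

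**5. Significance gate.** Keeping only runs with a significant mean difference (two-sided 0.05) changes little. The SD of c is 0.44 (Hb, 33 vs 33), 0.38 (HbO2, 33 vs 33) and 0.44 (HbO2, 11 vs 11).

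**6. What reaches study group 2.** With a fresh group 2 of 33 vs 33 and d = 0.62, observed sensitivity has SD 0.187 over repeats of the whole study. The part due to the cutpoint has SD 0.168, a variance share of 0.168²/0.187² ≈ 81%. For d = 1.10 the share is about 73%. For the Youden index in group 2 the cutpoint supplies only 5% to 8% of the variance across all scenarios.

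**7. Is an interval feasible?** Over 200 runs per scenario, the percentile bootstrap 95% interval covered the true cutpoint in 96% (Hb, 33 vs 33), 95% (HbO2, 33 vs 33) and 91% (HbO2, 11 vs 11). Median widths were 1.56, 1.35 and 1.54 SD. All exceed the distance between the group means: 1.56/0.62 = 2.5 times, 1.35/1.10 = 1.2 times and 1.54/1.10 = 1.4 times.

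**The case against.** **The validation already deals with this.** A reader might infer from the table that study group 2 mostly tests sampling noise. The documents do not support that. SAP 9.3 fixes the cutpoint before group 2 is analysed, so group 2 estimates the accuracy of that rule without bias and its intervals are valid for that rule. The loss in discrimination is also small. At 33 vs 33 the mean true Youden index is 0.243 − 0.219 = 0.024 (Hb) or 0.418 − 0.392 = 0.026 (HbO2) below optimum. This part of the objection stands.

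**The estimator should not simply be replaced.** A reader might infer that a Box-Cox-normal cutpoint ought to become primary. In simulations from smooth distributions it was more precise: at 33 vs 33 with normal data, the sensitivity range was 57–84% against 43–91% for HbO2. But mean true Youden index rose only from 0.39 to 0.41. If the PAD III/IV class is a mixture, which is plausible but assumed, the model-based cutpoint can sit further from the optimum: 0.4 to 0.55 SD away against 0.2 to 0.4 for the empirical one. Log and Box-Cox transformations also fail for the planned HbO2/Hb difference when it is zero or negative. This supports it as a sensitivity analysis only.

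**The inputs are assumed.** The effect sizes are back-solved, the 33 and 11 come from an illustrative calculation for mean differences, and the SAP leaves the Youden estimator open. All true. Yet the empirical cutpoint is imprecise in every scenario tried, and the missing interval is a fact of the text that needs no simulation.

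**The study is explorative.** That lowers the stakes but does not remove the need to show how precise the primary result is.

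**Conclusion.** The point holds in this form: the primary endpoint would be reported without any measure of precision, and under plausible inputs that precision is poor. The SD of the empirical Youden cutpoint is about 0.3 to 0.5 control SDs, and 0.63 if Hb were studied at only 11 vs 11. True sensitivity at the selected cutpoint can lie anywhere from roughly 30% or 45% (Hb or HbO2) to 90% at 33 vs 33, and the range is only slightly narrower at 40 vs 80. Chance in study group 1 drives the threshold value and the sensitivity/specificity split. It does not much affect overall discrimination or the validity of group 2 as a test of the chosen rule.

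The sizes rest on normal data with equal variances, effects back-solved from the SAP's own numbers, and an empirical Youden maximum. The omission of the interval rests on none of these.

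**What to change.** In SAP 9.3:

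- State that the cutpoint is the maximum of the empirical Youden index in study group 1, and name the rule for tied maxima.
- Report it with a bootstrap 95% confidence interval as the primary endpoint result. Resample controls and PAD III/IV separately, and re-select the cutpoint in every resample.
- Prespecify a smoothed or binormal Youden cutpoint as a sensitivity analysis. Use a transformation only for readouts that are strictly positive.
- Carry the single group 1 cutpoint into study group 2 unchanged, as now planned.

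Report the numbers of controls and PAD III/IV patients in study group 1 beside the interval, since coverage was somewhat low (91%) at 11 vs 11.

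The cost is SAP wording and a few lines of R, which SAP 11 already names; no new subjects or measurements are needed. The visible downside is a wide interval around the threshold.

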## 10 Reporting Convention

P-values  $\geq 0.001$  will be reported to 3 decimal places; p-values less than 0.001 will be reported as " $<0.001$ ". Non-significant P-values ( $>0.05$ ) will be reported to 2 decimal places. The mean and standard deviation will be reported to one decimal place greater than the original data. Quantiles, such as median, or minimum and maximum will use the same number of decimal places as the original data. Estimated parameters, not on the same scale as raw observations (e.g. regression coefficients) will be reported to 3 significant figures.

